7.6 Long Term Follow-up

Following the SFU visit, there will be long-term follow-up portion of the study for disease status and OS. Subjects will be followed via clinical visit or telephone contact every 3 months (± 1 month) after their SFU visit until death has been observed or a maximum of 2 years after start of treatment, whichever occurs first. Subjects will allow Amgen continued access to medical records, so that information related to subjects' health condition including disease status and OS may be obtained.

The following procedures will be completed for subjects who remain in remission (including subjects who have undergone alloHSCT) at each visit:

- Bone marrow aspirate/biopsy (morphological assessment only)
 - every effort should be made to perform BM aspirate/biopsy until relapse is confirmed
- Hematology with differential
- Documentation of concomitant medications limited to only anti-leukemic treatments
- Disease/Survival status

The following procedures will be completed for subjects who did not respond to or relapsed after protocol-specified therapy and are being followed in long-term follow-up:

- Telephone contact to determine survival status by either the research investigational site or treating physician.
- Documentation of concomitant medications limited to only anti-leukemic treatments

If B-cell counts have not recovered at the SFU visit (recovered is defined as number of CD19-positive cells per μL is 90 to 570), another sample will also be taken 6 months (+3 months) after SFU visit for determination of lymphocyte subsets ([Section 7.2.17](#)).

Should a subject fail to return to the clinic for a scheduled protocol visit, sites will need to make 3 attempts to contact subjects by a combination of telephone and mail. Sites must document all 3 attempts to contact the subject. If a subject does not respond within 1 month after the third contact, the subject will be considered lost to follow-up and no additional contact will be required.

7.7 End of Study

The end of study visit is defined as the date of the final study visit (eg, long-term follow-up) when assessments and/or procedures are performed.

7.8 Antibody Testing Procedures

Blood samples will be collected at timepoints as outlined in the Schedule of Assessments ([Table 9](#)) for the measurement of anti-blinatumomab binding antibodies. Samples testing positive for binding antibodies may be further characterized for quantity/titer, isotype, affinity, in vitro neutralizing activity, and presence of immune complexes. Additional blood samples may be obtained to rule out anti-drug antibodies during the study.

Subjects who test positive for binding antibodies and have clinical sequelae that are considered potentially related to an anti-blinatumomab antibody response may also be asked to return for additional follow-up testing.

7.9 Sample Storage and Destruction

Any blood sample collected according to the Schedule of Assessments ([Table 9](#)) can be analyzed for any of the tests outlined in the protocol and for any tests necessary to minimize risks to study subjects. This includes testing to ensure analytical methods produce reliable and valid data throughout the course of the study. This can also include, but is not limited to, investigation of unexpected results, incurred sample reanalysis, and analyses for method transfer and comparability.

All samples and associated results will be coded prior to being shipped from the site for analysis or storage. Samples will be tracked using a unique identifier that is assigned to the samples for the study. Results are stored in a secure database to ensure confidentiality.

The subject retains the right to request that the sample material be destroyed by contacting the investigator. Following the request from the subject, the investigator is to provide the sponsor with the required study and subject number so that any remaining blood samples and any other components from the cells can be located and destroyed. Samples will be destroyed once all protocol-defined procedures are completed. However, information collected from samples prior to the request for destruction, will be retained by Amgen.

The sponsor is the exclusive owner of any data, discoveries, or derivative materials from the sample materials and is responsible for the destruction of the sample(s) at the request of the subject through the Investigator, at the end of the storage period, or as appropriate (eg, the scientific rationale for experimentation with a certain sample type no longer justifies keeping the sample). If a commercial product is developed from this research project, the sponsor owns the commercial product. The subject has no commercial rights to such product and has no commercial rights to the data, information, discoveries, or derivative materials gained or produced from the sample.

See [Section 11.3](#) for subject confidentiality.

8. WITHDRAWAL FROM TREATMENT, PROCEDURES, AND STUDY

8.1 Subjects' Decision to Withdraw

Subjects have the right to withdraw from the study at any time and for any reason without prejudice to their future medical care by the physician or at the institution.

Subjects (or a legally acceptable representative) can decline to continue receiving investigational product and/or other protocol-required therapies or procedures at any time during the study but continue participation in the study. If this occurs, the investigator is to discuss with the subject the appropriate processes for discontinuation from investigational product or other protocol-required therapies and must discuss with the subject the options for continuation of the Schedule of Assessments ([Table 9](#)), including different options of follow-up (eg, in person, by phone/mail, through family/friends, in correspondence/communication with other treating physicians, from the review of medical records) and collection of data, including endpoints and adverse events. Subjects who have discontinued investigational product and/or protocol-required

therapies or procedures should not be automatically removed from the study. Whenever safe and feasible it is imperative that subjects remain on-study to ensure safety surveillance and/or collection of outcome data. The investigator must document the level of follow-up that is agreed to by the subject.

Withdrawal of consent for a study means that the subject does not wish to receive further protocol-required therapies or procedures, and the subject does not wish to or is unable to continue further study participation. Subject data up to withdrawal of consent will be included in the analysis of the study, and where permitted, publically available data can be included after withdrawal of consent. The investigator is to discuss with the subject appropriate procedures for withdrawal from the study.

8.2 Investigator or Sponsor Decision to Withdraw or Terminate Subjects' Participation Prior to Study Completion

The investigator and/or sponsor can decide to withdraw a subject(s) from investigational product and/or other protocol-required therapies, protocol procedures, or the study as a whole at any time prior to study completion.

Subjects may be eligible for continued treatment with Amgen investigational product(s) and/or other protocol-required therapies by a separate protocol or as provided for by the local country's regulatory mechanism, based on parameters consistent with [Section 12.1](#).

8.3 Reasons for Removal From Treatment or Study

8.3.1 Reasons for Removal From Treatment

Reasons for removal from protocol-required investigational product(s) or procedural assessments include any of the following:

- Protocol-specified criteria:
 - Hematological or extramedullary relapse subsequent to CR/CRh*/CRi on protocol treatment
 - Failure to achieve a BM response defined as $\leq 5\%$ blasts within 2 complete treatment cycles
 - Investigator decision that a change of therapy (eg, immediate HSCT) is in the subject's best interest
- subject request
- safety concern (eg, due to toxicity of protocol-specified therapy or other adverse event)
- decision by sponsor (other than subject request or safety concern)

- death
- lost to follow-up

8.3.2 Reasons for Removal From Study

Reasons for removal of a subject from the study are:

- decision by sponsor
- withdrawal of consent from study
- death
- lost to follow-up

At the time of the primary analysis and/or at the end of the long-term follow-up portion of the study, sites may be asked to conduct searches of public records, such as those establishing survival status, if available, to obtain survival data for any subject for whom the survival status is not known.

9. SAFETY DATA COLLECTION, RECORDING, AND REPORTING

9.1 Definition of Safety Events

9.1.1 Disease Related Events

Disease Related Events are events (serious or non-serious) anticipated to occur in the study population due to the underlying disease. Please refer to [Appendix D](#) for disease related events by system organ class. Such events do not meet the definition of an Adverse Event unless assessed to be more severe than expected for the subject's condition. All serious disease-related events will be recorded and reported to the sponsor or designee within 24 hours.

Disease-related events that would qualify as an adverse event or serious adverse event:

- An event based on the underlying disease that is worse than expected as assessed by the investigator for the subject's condition or if the investigator believes there is a causal relationship between the investigational product(s)/study treatment/protocol-required therapies and disease worsening, this must be reported as an adverse event or serious adverse event.

Disease Related Events and/or Disease Related Outcomes that do not qualify as Serious Adverse Events:

- An event which is part of the normal course of disease under study (eg, disease progression in oncology or hospitalization due to disease progression) is to be reported as a Disease Related Event.
- Death due to the disease under study is to be recorded on the Event eCRF.

9.1.2 Adverse Events

An adverse event is any untoward medical occurrence in a clinical study subject irrespective of a causal relationship with study treatment. The investigator is responsible for ensuring that any adverse events observed by the investigator or reported by the subject are recorded in the subject's medical record.

The definition of adverse events includes worsening of a pre-existing medical condition. Worsening indicates that the pre-existing medical condition or underlying disease (eg, diabetes, migraine headaches, gout) has increased in severity, frequency, and/or duration more than would be expected, and/or has an association with a significantly worse outcome than expected. A pre-existing condition that has not worsened more than anticipated (ie, more than usual fluctuation of disease) during the study or involves an intervention such as elective cosmetic surgery or a medical procedure while on study, is not considered an adverse event.

If the severity of an adverse event changes from the date of onset to the date of resolution, record as a single event with the worst severity on the Event eCRF.

For situations when an adverse event or serious adverse event is due to ALL, report all known signs and symptoms. Death due to disease progression in the absence of signs and symptoms should be reported as the primary tumor type (eg, relapsed/refractory B-precursor ALL).

Note: The term "disease progression" should not be used to describe the disease related event or adverse event.

"Lack of efficacy" or "failure of expected pharmacological action" will not be reported as an adverse event or serious adverse event. Such instances will be captured in the efficacy assessment. However, the signs, symptoms, and/or clinical sequelae resulting from lack of efficacy will be reported as adverse event or serious adverse event if they fulfill the definition of an adverse event or serious adverse event.

The investigator's clinical judgment is used to determine whether a subject is to be removed from treatment due to an adverse event. In the event a subject, or subject's legally acceptable representative requests to withdraw from protocol-required therapies or the study due to an adverse event, refer to [Section 8](#) for additional instructions on the procedures recommended for safe withdrawal from protocol-required therapies or the study.

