9.2.2 Adverse Events

9.2.2.1 Reporting Procedures for Adverse Events That Do not Meet Serious Criteria

The investigator is responsible for ensuring that all adverse events observed by the investigator or reported by the subject that occur after protocol-required therapies through the SFU visit are reported using the Event eCRF. Adverse events related to obligatory pre-medication as well as adverse events related to study procedures during the screening period will be reported on the Event eCRF. If any other anti-leukemic therapy is started within 30 days after last administration of blinatumomab, subsequently only adverse events assessed as being related to blinatumomab will be reported. During the long-term follow-up period, only adverse events assessed as related to blinatumomab or study procedures will be recorded.

The investigator must assign the following adverse event attributes:

- Adverse event diagnosis or syndrome(s), if known (if not known, signs or symptoms),
- Dates of onset and resolution (if resolved),
- Severity [and/or toxicity per protocol],

- Assessment of relatedness to blinatumomab, and
- Action taken.

The adverse event grading scale used will be the CTCAE version 4.03. The grading scale used in this study is described in [Appendix A](#). The investigator must assess whether the adverse event is possibly related to blinatumomab. This relationship is indicated by a “yes” or “no” response to the question: Is there a reasonable possibility that the event may have been caused by investigational product (blinatumomab) or other protocol-required therapies?

The investigator must assess whether the adverse event is possibly related to any study-mandated activity (eg, administration of investigational product, protocol-required therapies, device(s) and/or procedure (including any screening procedure(s))). This relationship is indicated by a “yes” or “no” response to the question: “Is there a reasonable possibility that the event may have been caused by a study activity (eg, administration of investigational product, protocol-required therapies, device(s)), and/or procedure”?

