9.2.2.2 Reporting Procedures for Serious Adverse Events

The investigator is responsible for ensuring that all serious adverse events observed by the investigator or reported by the subject that occur during the entire study period including the screening period (from the signing of the informed consent) through the SFU visit are recorded in the subject’s medical record and are submitted to Amgen. All serious adverse events must be submitted to Amgen within 24 hours following the investigator’s knowledge of the event via the Event CRF.

Approved

If the electronic data capture (EDC) system is unavailable to the site staff to report the serious adverse event, the information is to be reported to Amgen via an electronic Serious Adverse Event Contingency Report Form within 24 hours of the investigator's knowledge of the event. See [Appendix B](#) for a sample of the Serious Adverse Event Worksheet/electronic Serious Adverse Event Contingency Report Form. For EDC studies where the first notification of a Serious Adverse Event is reported to Amgen via the electronic Serious Adverse Event Contingency Report Form, the data must be entered into the EDC system when the system is again available.

The investigator must assess whether the serious adverse event is possibly related to any study-mandated activity or procedure. This relationship is indicated by a "yes" or "no" response to the question: "Is there a reasonable possibility that the event may have been caused by a study activity/procedure"?

The investigator is expected to follow reported serious adverse events until resolution, stabilization of the condition, or until the subject is lost to follow-up.

New information relating to a previously reported serious adverse event must be submitted to Amgen. All new information for serious adverse events must be sent to Amgen within 24 hours following knowledge of the new information. The investigator may be asked to provide additional follow-up information, which may include a discharge summary or extracts from the medical record. Information provided about the serious adverse event must be consistent with that recorded on the Event eCRF.

If a subject is permanently withdrawn from protocol-required therapies because of a serious adverse event, this information must be submitted to Amgen.

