Appendix B. Sample Serious Adverse Event Report Form

Completion Instructions - Electronic Adverse Event Contingency Report Form (For use for clinical trial studies using Electronic Data Capture [EDC])

NOTE: This form is to be used under restricted conditions outlined on page 1 below. If you must fax an event report to Amgen, you must also enter that event into the EDC system (eg, Rave) when it becomes available.

General Instructions

The protocol will provide instruction on what types of events to report for the study. This form is to be used **ONLY** to report events that must be captured in the Amgen safety database. *Indicates a mandatory field.

Types of Events to be reported on this form

- Serious Adverse Events (regardless of causal relationship to IP)

1. Site Information

Site Number* – Enter your assigned site number for this study

Investigator*, Country*, Reporter*, Phone No., and Fax No. – Enter information requested

2. Subject Information

Subject ID Number* – Enter the entire number assigned to the subject

Age at event onset, Sex, and Race – Enter the subject's demographic information

End of Study date – If the subject has already completed the study or terminated the study early, enter the End of Study date

If you are submitting follow-up information to a previous report, provide the serious adverse event term for the previous report as well as the start date for the initial event.

3. Serious Adverse Event

Provide the date the Investigator became aware of this Information

Serious Adverse Event Diagnosis or Syndrome* –

- If the diagnosis is known, it should be entered. Do not list all signs/symptoms if they are included in the diagnosis.
- If a diagnosis is not known, the relevant signs/symptoms should be entered.
- If the event is fatal, the cause of death should be entered and autopsy results should be submitted, when available.

Date Started* – Enter date the adverse event first started (not the date on which the event met serious criteria) rather than the date of diagnosis or hospitalization. **This is a mandatory field.**

Date Ended – Enter date the adverse event ended and not the date when the event no longer met serious criteria. If the event has not ended at the time of the initial report, a follow-up report should be completed when the end date is known. If the event is fatal, enter the date of death as the end date.

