If event occurred before the first dose of Investigational Product (IP)/drug under study, add a check mark in the corresponding box.

Is event serious?* – Indicate Yes or No. **This is a mandatory field.**

Serious Criteria Code* – **This is a mandatory field for serious events.** Enter all reasons why the reported event has met serious criteria:

- Immediately life-threatening – Use only if the subject was at immediate risk of death from the event as it occurred. Emergency treatment is often required to sustain life in this situation.
- If the investigator decides an event should be reported in an expedited manner, but it does not meet other serious criteria, "Other Medically Important Serious Event" may be the appropriate serious criterion.

Relationship to IP – The Investigator must determine and enter the relationship of the event to the IP at the time the event is initially reported. **This is a mandatory field.**

Relationship to Amgen device* – The Investigator must determine and enter the relationship of the event to the Amgen device (e.g. prefilled syringe, auto-injector) at the time the event is initially reported. **If the study involves an Amgen device, this is a mandatory field. This question does not apply to non-Amgen devices used in the study (e.g. heating pads, infusion pumps)**

Outcome of Event* – Enter the code for the outcome of the event at the time the form is completed. **This is a mandatory field.**

- Resolved – End date is known
- Not resolved / Unknown – End date is unknown
- Fatal – Event led to death

If event is related to a study procedure, such as a biopsy, radiotherapy or withdrawal of a current drug treatment during a

**Completion Instructions - Electronic Adverse Event Contingency Report Form
(for use for Studies using Electronic Data Capture [EDC])**

Note, this form is to be used under restricted conditions outlined on page 1 of the form. If you must fax an event report to Amgen, you must also enter that event into the EDC system (eg, Rave) when it becomes available.

wash-out period, add a check mark to the corresponding box. This does not include relationship to IP or concomitant medication – only diagnostic tests or activities mandated by the protocol.

4. Hospitalization

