Prior salvage regimens are those medications recorded on the prior anti-cancer therapies CRF where the line of therapy field indicates salvage chemotherapy.

Protocol-specified Therapy

Protocol-specified therapy refers to the treatment blinatumomab. The protocol also uses the term “protocol required therapy” but for consistency protocol-specified therapy will be used throughout this document.

Relative Treatment Duration of Blinatumomab:

For each cycle, the relative treatment duration will be duration of blinatumomab infusion for that cycle divided by 28 days, the planned duration of infusion. For the entire study, the relative treatment duration will be the duration of blinatumomab infusion for the entire study divided by 28 times the number of cycles started. Re-started cycles will count as 28 days for the period before the re-start and 28 days for the period after the re-start in the calculation of planned duration.

Study Day 1

The first day of the infusion of blinatumomab.

Treatment-emergent Adverse Event

AEs starting on or after first dose of blinatumomab as determined by the flag indicating if the adverse event started prior to the first dose on event page of CRF and up to and including 30 days after the end of blinatumomab. This reporting window also applies to treatment-emergent serious adverse events (SAEs).

7. Analysis Sets

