10.6 Safety Analyses

10.6.1 Adverse Events

The Medical Dictionary for Regulatory Activities (MedDRA) version 20.0 or later will be used to code all adverse events (AE) to a system organ class and a preferred term. AEs of interest (EOI) categories will be based on search strategies defined by medical coding. Treatment-emergent adverse events are events with an onset after the administration of the first dose of Blinatumomab.

The subject incidence of AEs will be summarized for all treatment-emergent AEs, serious AEs, AEs leading to withdrawal of Blinatumomab, fatal AEs and EOI.

Subject incidence of all treatment-emergent AEs, serious AEs, AEs leading to withdrawal of IP, and fatal AEs will be tabulated by system organ class and preferred term in descending order of frequency; similar summaries will be repeated for EOs. Time to onset of selected EOs (infection, **cytokine release syndrome** and neurologic events) may also be summarized **with descriptive statistics. Duration of selected EOs will be summarized by KM methods and the descriptive statistics for resolved events (number of subjects; number of events; number of days experiencing events: mean, SD, median, Q1, Q3, min, max) and unresolved events (number of subjects, number of events) of selected EOs should also be provided.**

A summary of treatment-emergent AEs will be tabulated by system organ class, preferred term, and worst grade.

Subgroup analyses (if there is a medical or regulatory rationale) will be presented by system organ class and preferred term in descending order of frequency.

The number and percentage of subjects with antibody formation to blinatumomab will be summarized. In addition, changes in vital sign and laboratory parameters will be summarized.

Subject incidence of all disease related events, fatal disease related events, serious disease related events, and disease related events leading to withdrawal from blinatumomab, will also be provided.

Extent of exposure to blinatumomab will be summarized using descriptive statistics. Percentage of subjects and number of cycles with doses held and dose reductions will be calculated.

These analyses will be performed using subjects in the SAS.

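### An adverse event recorded before the first dose that worsens on blinatumomab drops out of the treatment-emergent incidence and worst-grade tables, because it stays one record and the SAP looks only at onset

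*Protocol*

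**What the plan says.** **Recording.** Protocol 9.1.2 (Adverse Events) says that if severity changes between onset and resolution, the site is to "record as a single event with the worst severity on the Event eCRF". The attributes listed in Protocol 9.2.2.1 are diagnosis, onset and resolution dates, severity, relatedness and action taken. A date of grade change is not among them. The sample serious AE form in Protocol Appendix B takes the date the event first began, not the date it became serious, and instructs: "If event occurred before the first dose of Investigational Product (IP)/drug under study, add a check mark in the corresponding box".

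**Collection before dosing.** For non-serious events, Protocol 9.2.2.1 names the Event eCRF as the form and states: "Adverse events related to obligatory pre-medication as well as adverse events related to study procedures during the screening period will be reported". Serious AEs are collected under Protocol 9.2.2.2 for the whole study, "including the screening period (from the signing of the informed consent) through the SFU visit".

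**Analysis.** SAP Section 6 defines treatment-emergent as "AEs starting on or after first dose of blinatumomab as determined by the flag indicating if the adverse event started prior to the first dose", with a window that closes 30 days after the end of blinatumomab. SAP 10.6.1 says: "Treatment-emergent adverse events are events with an onset after the administration of the first dose of Blinatumomab". SAP 10.6.1 also plans a table of treatment-emergent AEs by system organ class, preferred term and worst grade.

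**The concern.** An onset-only definition is safe if sites open a new record when an existing event worsens on drug. It is also safe if nothing is recorded before dosing. Neither holds here: the protocol asks for one record per event, and some pre-dose AEs are collected. The increase in grade on drug is then stored under a pre-dose onset, and the analysis filter removes it.

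The trial has one arm, so the treatment-emergent tables are the main description of safety and there is no control column in which a similar loss would show. A promising overall benefit-risk assessment is one of the conditions for the interim analysis to become the primary analysis (Protocol 10.3.1, SAP 8.1). Any error from this source can only lower the reported incidence or grade.

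**Working it through.** The plan states no figure on this point, so the check follows one record through the rules.

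1. **Entry.** During screening a subject has a serious AE, or a non-serious AE related to premedication or a study procedure, at grade 2. It goes on the Event eCRF (Protocol 9.2.2.1, 9.2.2.2). Such events can arise: Protocol 7.3 places the obligatory premedication in screening, and Protocol 6.4 schedules intrathecal prophylaxis in the 14 days before the start of blinatumomab.
2. **Worsening.** The event is still ongoing at first dose and reaches grade 4 on blinatumomab. Under Protocol 9.1.2 it remains one record, now with worst grade 4. The start date and pre-dose flag do not change.
3. **Filter.** SAP Section 6 tests the pre-dose flag, and the record fails. SAP 10.6.1 tests onset after first dose, and the record fails. The two definitions differ in detail (on or after first dose with a 30-day limit, against after first dose with no stated end), but neither has a clause for worsening.
4. **Result.** The grade 4 event is absent from the treatment-emergent incidence table and from the worst-grade table.

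**Search for a rescue clause.** Protocol 9.1.2 also counts worsening of a pre-existing medical condition as an AE. Its examples are diabetes, migraine and gout, that is, medical history. It does not clearly override the single-record sentence for an event already recorded as an AE. SAP Appendix A imputes the first-dose date for some partial or missing start dates, but does nothing for a complete pre-dose date. No other section restores the event.

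**Size per subject.** If the subject has no other qualifying event in the row:
- all subjects: 1/120 = 0.83 percentage points;
- Interim Analysis Set: 1/90 = 1.11 percentage points.

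If the subject has another, milder on-drug event under the same term, the incidence row is unchanged but the worst grade is understated.

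The number of affected subjects cannot be derived from the documents.

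**The case against.** The strongest reply is that few events can take this route. Most of that reply stands.

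- **Neurological events.** Under Protocol 7.2.8, abnormalities present at screening are medical history and new findings during the study are AEs. Worsening of such an abnormality would normally be a new AE with on-drug onset, and counted.
- **Infections.** Protocol Appendix D lists infection terms as disease-related. Under Protocol 9.1.1 these are not AEs unless worse than expected or causally linked to study treatment. Protocol 9.2.1 records disease-related events only after the first dose, and they have their own summaries. Only an infection attributed to protocol therapy, or judged worse than expected, could enter before dosing.
- **Procedures.** Protocol 7.3 treats standard-of-care lumbar puncture and marrow sampling as not study specific, and Protocol 6.4 lets intrathecal prophylaxis be omitted for safety reasons. A reader might infer that every subject is exposed; the text does not establish that.
- **Fatal cases.** A reader might infer that fatal worsening is certainly lost. Protocol 10.4.5 and SAP 10.6.1 list serious and fatal AE tables without a clear treatment-emergent limit, although SAP Section 6 does speak of treatment-emergent serious AEs. A fatal case may still appear there.
- **Recovery.** A reader might infer that nothing can be reconstructed. Appendix B makes the end date of a fatal event the date of death, so fatal worsening can be identified. For non-fatal increases, the lack of a date of worsening is inferred from the listed attributes; the eCRF completion guidelines are not in the documents.
- **Overall incidence.** In the two earlier studies 224 of 225 subjects (99.6%) had at least one treatment-emergent AE, so the any-event row would hardly move. The effect falls on rows for individual terms and grades.

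These points narrow the route but do not close it. A serious AE that begins in screening, or a premedication-related AE, still enters the database before dosing and is still filtered out if it worsens.

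**Conclusion.** The point holds in a limited form. As written, the recording rule and the onset-only definitions together exclude on-drug worsening of an AE already recorded before first dose from the treatment-emergent incidence and worst-grade tables. The direction is downward. The size is 0.83 points per affected subject per row at 120 subjects and 1.11 points at 90, given no other qualifying event in that row.

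This assumes that sites follow Protocol 9.1.2 literally and that the eCRF guidelines do not already ask for a new record.

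The total effect is unknown. It is tempting to size it from the 68.8% of subjects with high marrow blasts in the cited phase 2 study (0.688 × 120 = 82.6, about 83 subjects), since a blast proportion above about 50% makes pre-phase dexamethasone mandatory. That figure counts exposure to a steroid, not AEs that worsen. It also comes from a population in which 41% + 39% = 80% were treated third-line or later, whereas about half of this trial is to be in first salvage. It should not be used as an estimate of affected subjects.

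**What to change.** 1. **SAP Sections 6 and 10.6.1.** Use one definition in both places: onset on or after first dose, or onset before first dose with an increase in CTCAE grade on or after first dose, within the existing 30-day window.
2. **Protocol 9.1.2 and eCRF completion guidelines.** When a pre-dose AE increases in grade after first dose, open a new record dated at the worsening.
3. **Records already entered.** For AEs flagged as pre-dose and ongoing at first dose, query sites for the grade at first dose and the date of any worsening. Count those with a fatal outcome after first dose as treatment-emergent; the end date already identifies them. The date on which an event became serious cannot serve as the key, because the sample form does not record it.
4. **SAP 10.6.1.** State whether the serious and fatal AE tables are limited to treatment-emergent events.

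The cost is a few sentences of text, one site instruction and a small query round. Treatment-emergent incidence may become slightly higher. Treatment and the efficacy analysis are unaffected.
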